#### 6.1.8.10 HEPATOTOXICITY

Pomalidomide hepatotoxicity is rare. Elevations in bilirubin or transaminases > 3 times the baseline value should prompt temporary discontinuation of pomalidomide. Laboratory testing should be

performed two weeks after discontinuation to assure that abnormalities have resolved. If so, therapy may be resumed at a dose of 3 mg/day.

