#### 6.1.8.11 RENAL TOXICITY

Renal toxicity of pomalidomide is rare. Renal toxicity is defined by CTCAE version 4.0 criteria. An increase of creatinine of  $> 0.3$  mg/dl, or a baseline creatinine  $> 1.5$  with an increase at least 2x above baseline define Grade 1 nephrotoxicity. If these abnormalities are confirmed, the pomalidomide dose should be reduced to 3 mg/day. For higher levels of nephrotoxicity, the drug will be discontinued until the abnormalities have resolved and pomalidomide will then be reintroduced at a dose of 3.0 mg/day.

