##### **Complete Metabolic Profile**

A complete metabolic profile including renal and liver function studies will be performed at screening, at the initiation of therapy, each month during pomalidomide therapy, and at the end of treatment. The ALT, AST, alkaline phosphatase, total bilirubin, creatinine and BUN at all study visits will be recorded.

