4.2 Study Population

The study population is defined by the following eligibility criteria.

Inclusion Criteria:

1. A clinical diagnosis of HHT as defined by the Curacao criteria
2. Age > 18 years
3. Platelet count $\geq 100 \times 10^9/L$
4. WBC $\geq 2.5 \times 10^9/L$
5. INR ≤ 1.4 and normal ± 2 sec activated partial thromboplastin time (aPTT or PTT per local laboratory designation) by local laboratory criteria (except for patients on a stable dose of warfarin or direct oral anticoagulants)
6. Epistaxis severity score ≥ 3 measured over the preceding three months, measured at the screening visit
7. A requirement for anemia, as determined by local laboratory hemoglobin assessment and normal ranges, and/or parenteral infusion of at least 250 mg of iron or transfusion of 1 unit of blood over the 24 weeks preceding the screening visit
8. All study participants must agree to be registered into the FDA mandated POMALYST REMS® program, and be willing and able to comply with the requirements of the POMALYST REMS® program
9. Females of childbearing potential (FCBP) must adhere to the pregnancy testing schedule mandated by the POMALYST REMS® program.
10. Ability to understand and sign informed consent

Exclusion Criteria:

1. Women currently breast feeding or pregnant
2. Renal insufficiency, serum creatinine > 2.0 mg/dl
3. Hepatic insufficiency, bilirubin > 2.0 (or > 4.0 in the setting of a prior clinical or genetic diagnosis of Gilbert's syndrome) or transaminases $> 3.0 \times$ normal
4. Prior treatment with thalidomide or other Immunomodulatory imide drugs (IMiDs) within previous 6 months
5. Prior treatment with bevacizumab (systemic or nasal) within previous 6 weeks
6. Prior treatment with pazopanib within previous 6 weeks
7. The use of octreotide or oral estrogens within the previous month
8. History of prior unprovoked thromboembolism confirmed by venous ultrasound or other imaging modalities
9. Known peripheral neuropathy, confirmed by neurologic consultation
10. Known underlying hypoproliferative anemia (i.e., myelodysplasia, aplastic anemia)
11. Currently enrolled in other interventional trials
12. Known hypersensitivity to thalidomide or lenalidomide.
13. The development of erythema nodosum if characterized by a desquamating rash while taking thalidomide or similar drugs.
14. Known SMAD-4 mutation
15. Anything that in the investigator's opinion is likely to interfere with completion of the study

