10.4 Laboratory Evaluations

Laboratory exams (include blood chemistry and hematology) will be collected from each patient and will be summarized by study visit. Box and whisker plots will be generated to show the changes across study visits for key safety labs. These have been produced for the DSMB reports.

If applicable, linear mixed effect models will be constructed modeling change from baseline for key safety lab values over time with study time treated categorically and will be used to compare any post-baseline measures to baseline. Change from baseline will be assessed for substantial violations of normality and if so, a transformation will be considered.

Incidence of treatment-emergent abnormal safety labs at any post-baseline timepoint for all collected lab parameters will be tabulated (similar to that produced for the DSMB reports but DSMB was not focused on treatment-emergent labs), and treatment groups will be compared with chi-squared or Fisher's exact test, if applicable. Treatment-emergent abnormal is defined as a lab value post-baseline that is outside the normal range during the treatment period but is within the normal range at baseline (or at screening, if the baseline value is missing).

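### SAP 10.4's treatment-emergent lab flag sets no direction or size and never counts a patient on a liver or renal parameter that was abnormal at baseline, although such patients are eligible

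*SAP*

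**What the plan says.** SAP 10.4 defines the flag in two parts. The first: "Treatment-emergent abnormal is defined as a lab value post-baseline that is outside the normal range during the treatment period". The second: "but is within the normal range at baseline (or at screening, if the baseline value is missing". Incidence at any post-baseline time is tabulated for all lab parameters, and the arms are compared by chi-squared or Fisher's exact test where applicable. The section also plans visit summaries, box plots for key safety labs and, if applicable, mixed models. Those models "will be used to compare any post-baseline measures to baseline"; no between-arm contrast is stated for them.

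Entry does not require normal values. The relevant exclusions in SAP 4.2, matching Protocol 5.2, are "Renal insufficiency, serum creatinine > 2.0 mg/dl" and "Hepatic insufficiency, bilirubin > 2.0 (or > 4.0 in the setting of a prior clinical or genetic diagnosis of" Gilbert's syndrome, or transaminases above 3.0 times normal. Anyone at or below these limits may enrol.

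The protocol's dosing rules work from the patient's own baseline. For the liver (6.1.8.10): "Elevations in bilirubin or transaminases > 3 times the baseline value should prompt temporary discontinuation of pomalidomide". For the kidney (6.1.8.11), Grade 1 is a creatinine rise above 0.3 mg/dl, or a baseline above 1.5 "with an increase at least 2x above baseline define Grade 1 nephrotoxicity. If these abnormalities are confirmed, the pomalidomide dose should be reduced". Higher grades under CTCAE 4.0 stop the drug until they resolve.

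The data exist (Protocol 7.2.1.1): "The ALT, AST, alkaline phosphatase, total bilirubin, creatinine and BUN at all study visits will be recorded".

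**The concern.** Safety and tolerability is the first secondary objective, and hepatotoxicity is among the risks listed in Protocol 2.3.1. Two features of the definition limit what the planned table can show.

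- **Baseline condition.** A patient out of range at baseline on a parameter drops out of the numerator for that parameter, however much it worsens. These may be the patients in whom a further rise matters most.
- **No direction or size.** A low creatinine counts like a high one, and an ALT just over the limit counts like a five-fold rise.

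A reader of the final report could not tell from this table how many patients per arm reached a liver or renal value at which the protocol holds or cuts the drug.

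**Working it through.** The plan states no figure on this point, so there is none to reproduce. The check applies the stated definition and the stated dosing rules to the same values.

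**1. What follows from the documents alone.** The flag requires baseline in [L, U] and a later value outside [L, U]. If baseline is above U, the flag is always no.
- Transaminases: entry at 3 × normal; the hold threshold is 3 × baseline; 3 × 3 = 9 × normal. Never flagged.
- Bilirubin: entry at 2.0 gives 3 × 2.0 = 6.0; with Gilbert's syndrome, 3 × 4.0 = 12.0. Never flagged where these entry values exceed the local limit.
- Creatinine: entry at 1.6 mg/dl doubles to 3.2 mg/dl. Never flagged if the local upper limit is below 1.6. Where that limit is 1.5 or lower, nobody in the protocol's baseline-above-1.5 group can be flagged on creatinine.

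**2. Flag against threshold on example values.** Reference ranges are assumed, because the documents use local ranges: ALT 7-40, bilirubin 0.2-1.2, creatinine 0.6-1.2.

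| Baseline → on treatment | SAP flag | Protocol threshold |
|---|---|---|
| ALT 60 → 190 | no | met (3 × 60 = 180) |
| Bilirubin 1.8 → 5.6 (Gilbert's) | no | met (3 × 1.8 = 5.4) |
| Creatinine 1.6 → 3.3 | no | met (rise 1.7) |
| Creatinine 1.4 → 1.8 | no | met (rise 0.4) |
| ALT 8 → 6 | yes | not met |
| ALT 38 → 44 | yes | not met |
| ALT 30 → 95 | yes | met (3 × 30 = 90) |

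**3. How many patients cannot be counted.** The documents give no baseline-abnormal rate. At an assumed 5%, 10% or 20% on a parameter, with the planned arms:
- pomalidomide: 106 × (0.05, 0.10, 0.20) = 5.3, 10.6, 21.2;
- placebo: 53 × (0.05, 0.10, 0.20) = 2.7, 5.3, 10.6.

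**4. Why direction matters.** Assume the normal range is the central 95%, with six treatment visits and no drug effect. With independent visits, 1 − 0.95^6 = 0.265 of baseline-normal patients are flagged on a parameter. Of these, (0.975^6 − 0.95^6)/0.265 = (0.859 − 0.735)/0.265 = 0.47 have only low values. Independence is not realistic for repeated labs. Simulation (10^6 patients, exchangeable normal values) gives 19% flagged at within-patient correlation 0.5 and 7% at 0.9, half of them low only.

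**5. Rises that stay in range.** A baseline-normal patient can also meet a threshold without leaving the range. For a lognormal parameter whose range is the central 95%, the share still in range at multiple m is [Φ((ln(U/m) − μ)/σ) − 0.025]/0.95. For ALT just over 3 × baseline this is 11% (range 10-40) to 45% (range 7-55); at 5 × it is 0% to 12%. For a creatinine rise just over 0.3 mg/dl, the normal-distribution equivalent is 50% (0.6-1.2) to 62% (0.6-1.3). Many of these rises would be clinically minor, so this is the least important of the mismatches.

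**6. Is a separate baseline-above-1.5 row needed?** No. Reaching at least 2 × a baseline above 1.5 is a rise of more than 1.5 mg/dl, which already exceeds 0.3.

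**The case against.** The strongest reply is that the adverse event route already covers this. Protocol 8.1.1 counts an abnormal laboratory finding as an adverse event. Protocol 8.3 requires all events to be documented, and a condition present at screening that deteriorates must be recorded. SAP 10.2 tabulates events by arm and severity, SAP 10.1 compares incidence, and SAP 9.2 names ALT increased as a specific term after blinded review. Visit summaries give ranges (SAP 7.1), so an ALT of 9 times normal would appear as a maximum. SAP 8.3 shows dose levels by arm. All of this stands and narrows the point. But the event route still depends on a site judging and reporting a lab change, no bilirubin, AST or creatinine term is named, a visit maximum does not count patients, and the dose table gives no cause.

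The table shells and the DSMB lab tables, on which the flag table is modelled, are not available here. They may already split high from low. That would not bring back baseline-abnormal patients under the definition as written.

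A reader might also infer that the flag was meant to detect the dosing triggers and fails, or that liver and renal toxicity would go unseen. The documents support neither. SAP 10.4 never presents the flag as a trigger count, the protocol calls both toxicities rare, and investigators apply the dosing rules regardless of this table. Nor is the flag blind. Suppose 5% of pomalidomide patients (5.3 of 106) peaked at 3-5 times baseline ALT. Under the assumptions above, the flag would include about 3 to 5 of them, but unlabelled among 9 to 30 flagged patients.

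**Conclusion.** The point holds as a defect in a stated definition. Followed exactly, SAP 10.4 leaves on-treatment worsening in eligible, baseline-abnormal patients out of the only stated between-arm comparison of liver and renal lab values, and it mixes high with low and trivial with large excursions. This follows from the text of SAP 10.4 and Protocol 5.2 and needs no assumption.

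Its size does need assumptions: about 5 to 21 pomalidomide and 3 to 11 placebo patients per parameter if 5% to 20% are abnormal at baseline. The other percentages rest on assumed reference ranges, distributions and correlations and are illustrations only.

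The change should be made, but the gain is clearer descriptive safety reporting and nothing more. Power, the primary analysis and patient management are unaffected. There is a precedent: the platelet and neutrophil categories in SAP 9.2 use each patient's lowest post-baseline value with no baseline-normal condition.

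**What to change.** In SAP 10.4:

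- Report treatment-emergent high and treatment-emergent low values separately.
- For all treated patients with a baseline value, normal or not (screening if baseline is missing, as now), add descriptive counts by arm, without tests, of:
  - maximum on-treatment ALT, AST or bilirubin more than 3 times baseline (Protocol 6.1.8.10);
  - creatinine rise above 0.3 mg/dl (Protocol 6.1.8.11), with the higher CTCAE 4.0 grades that require stopping the drug as separate rows. Their cut-offs are printed in neither document and need writing in.
- List baseline, peak and upper limit of normal for each patient counted.

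Do not split creatinine rises into confirmed and unconfirmed. The protocol makes the dose cut depend on confirmation but does not define it, and a cut made before the next monthly sample could reverse a real rise. Label the row as meeting the numeric criterion, not as requiring a dose cut.

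The cost is a few table rows and one listing from values already recorded. SAP 14 allows displays to be added without amendment if they do not contradict the text. The drawback is that some 3-fold rises from low-normal values will be clinically minor, which is why the peak and the upper limit are listed.

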### 5.2 PARTICIPANT EXCLUSION CRITERIA

1. Women currently breast feeding or pregnant
2. Renal insufficiency, serum creatinine  $> 2.0 \text{ mg/dl}$
3. Hepatic insufficiency, bilirubin  $> 2.0$  (or  $> 4.0$  in the setting of a prior clinical or genetic diagnosis of Gilbert's syndrome) or transaminases  $> 3.0 \times \text{normal}$
4. Prior treatment with thalidomide or other Immunomodulatory imide drugs (IMiDs) within previous 6 months
5. Prior treatment with bevacizumab (systemic or nasal) within previous 6 weeks\*

6. Prior treatment with pazopanib within previous 6 weeks\*
7. The use of octreotide or oral estrogens within the previous month\*
8. History of prior unprovoked thromboembolism confirmed by venous ultrasound or other imaging modalities
9. Known peripheral neuropathy, confirmed by neurologic consultation
10. Known underlying hypoproliferative anemia (i.e. myelodysplasia, aplastic anemia)
11. Currently enrolled in other interventional trials
12. Known hypersensitivity to thalidomide or lenalidomide
13. The development of erythema nodosum if characterized by a desquamating rash while taking thalidomide or similar drugs
14. Known *SMAD-4* mutation, unless there has been a colonoscopy with normal (negative) results, or in which the patient has had no more than 5 small (in the opinion of the gastroenterologist) colonic polyps completely removed within the preceding 18 months
15. Anything that in the investigator's opinion is likely to interfere with completion of the study

\* Use of these treatments is not permitted during study participation. See protocol section 7.6 for additional details regarding prohibited treatments.

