Change from baseline in iron (transferrin) saturation, ferritin, hemoglobin, hematocrit, MCV, and MCHC.	Continuous	Lab parameters are analyzed at each site (including at local labs) and entered onto CRFS in the EDC system. Transferrin Saturation is calculated within medidata from Iron and Iron Binding Capacity.

Variable	Type	Definition
		The outcome will then be computed as the difference in value at each post-baseline visit and the value at baseline.
Thrombocytopenia platelet categories	Categorical Normal < 150 K/uL < 100 K/uL < 50 K/uL	Added as additional planned safety presentation at blinded data review meeting. Categorical assessment of thrombocytopenia will be calculated based on all platelets collected post-baseline. A person will be classified into one of the 4 categories based on the lowest recorded post-baseline platelet value. The value of 150 represents the lower normal bound.
Neutropenia neutrophils categories	Categorical Normal < 1.45 K/uL < 1.00 K/uL < 0.50 K/uL	Added as additional planned safety presentation at blinded data review meeting. Categorical assessment of neutropenia will be calculated based on all neutrophils collected post-baseline. A person will be classified into one of the 4 categories based on the lowest recorded post-baseline neutrophil value. The value of 1.45 represents the lower normal bound.
Exploratory Outcomes		
Relapse at 4-weeks post treatment	Dichotomous (Yes/No)	The rate of relapse will be calculated at 4 weeks post-treatment. Relapse is defined as a return of the ESS to the baseline value or greater.
Treatment weeks to 1.0 decrease in ESS	Ordinal Categorical (4, 8, 12, 16, 20, 24, Not obtained)	The time to the first 1.0-unit decrease in ESS will be calculated for each participant by computing the difference between the baseline ESS and the ESS at each study visit and determining the first study visit at which the difference is ≤ -1.0 , or “not obtained” if no visit had an improvement of at least 1.0

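### The treatment-emergent laboratory table in SAP 10.4 omits worsening from an abnormal baseline, leaving transaminases, bilirubin and creatinine without an objective count that includes such participants

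*SAP*

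**What the plan says.** SAP 10.4 commits to a broad table: "Incidence of treatment-emergent abnormal safety labs at any post-baseline timepoint for all collected lab parameters will be tabulated". Arms are to be compared by chi-squared or Fisher's exact test where applicable. An abnormality is treatment-emergent if the value is "outside the normal range during the treatment period but is within the normal range at baseline", or within range at screening when the baseline value is missing. Nothing provides for a value that starts abnormal and gets worse. SAP 10.1 assigns safety analyses to the whole safety population, but 10.4 does not say whether participants who cannot have an event stay in the denominator.

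The eligibility criteria (Protocol 5.1 and 5.2, repeated in SAP 4.2) allow abnormal values at entry:

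- Platelets are accepted from 100 x 10^9/L, whereas SAP 9.2 says of its platelet categories: "The value of 150 represents the lower normal bound".
- Transaminases exclude only above 3.0 times normal.
- Bilirubin excludes at "bilirubin > 2.0 (or > 4.0 in the setting of a prior clinical or genetic diagnosis of Gilbert's syndrome").
- Creatinine excludes at "Renal insufficiency, serum creatinine > 2.0 mg/dl".
- Anemia by local hemoglobin range is one of the qualifying routes, alongside iron infusion or transfusion.

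These limits apply at screening. Protocol 7.3.2 says that baseline laboratory results are not used to re-establish eligibility.

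**The concern.** A rule that needs a normal starting value measures crossings of the reference limit, not deterioration. A trivial crossing scores one event, and a severe fall or rise in a participant who was already outside the limit scores none. The participants left out are those with the least reserve for that organ or cell line.

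The protocol itself judges these organs against the participant's own starting value. Section 6.1.8.10 refers to bilirubin or transaminases more than 3 times baseline. Section 6.1.8.11 refers to creatinine rise and explicitly anticipates a raised baseline creatinine. A participant can therefore meet the protocol's own description of liver or renal toxicity and still add nothing to the SAP 10.4 table. At stake is how well that table shows individual laboratory toxicity by arm.

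**Working it through.** No figure in the plan depends on this definition, so there is none to reproduce. The check applies the rule to permitted values, then looks for cover elsewhere, then illustrates size.

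**1. Applying the rule.** Event = (baseline within range) and (on-treatment value out of range). The SAP 9.2 normal bounds are 150 for platelets and 1.45 for neutrophils (K/uL). Limits marked * are assumptions, because local ranges are not in the documents. Eligibility sets a white-cell floor but no neutrophil floor.

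| Analyte | Baseline to on-treatment | SAP 10.4 | Objective indicator in SAP 9.2 |
|---|---|---|---|
| Platelets | 160 to 140 | counted | category <150 |
| Platelets | 110 to 45 | not counted | category <50 |
| Neutrophils | 1.5 to 1.4 | counted | category <1.45 |
| Neutrophils | 1.3 to 0.4 | not counted | category <0.50 |
| ALT (x ULN) | 0.99 to 1.01 | counted | none |
| ALT (x ULN) | 2.9 to 10 | not counted | none |
| Creatinine (ULN 1.2*) | 1.9 to 5 | not counted | none |
| Hemoglobin (LLN 12*) | 9 to 6 | not counted | flagged as below 6.5 |

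The uncounted ALT case is 10 / 2.9 = 3.4 times baseline, above the threshold in Protocol 6.1.8.10. By Protocol Table 1A, the uncounted platelet case goes from grade 1 to grade 3 and the uncounted neutrophil case from grade 2 to grade 4, so a grade-based rule would count both.

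**2. Cover elsewhere.**

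- Platelets and neutrophils: SAP 9.2 classifies everyone by lowest post-baseline value, whatever the baseline. This catches the severe falls. It also puts an unchanged platelet count of 110 in the <150 category, so it does not separate worsening from a stable abnormality.
- Hemoglobin: change from baseline is a secondary outcome, and a value below 6.5 gm/dl in the treatment period is reported.
- Transaminases, bilirubin, creatinine: SAP 10.4 gives by-visit summaries and, for key safety labs, box plots and conditional mixed models of mean change. None of these counts individuals who worsened.

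**3. Illustrative size.** Let f be the share with an abnormal baseline for one analyte. The documents do not give f, so it is shown as a range. Assume true worsening of 20% versus 5% regardless of baseline, 106 versus 53 participants, and two-sided alpha 0.05.

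Tabulated incidence with everyone in the denominator: p_A = 0.20(1 - f), p_P = 0.05(1 - f).

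Power = Phi[(d - 1.96 x se0) / se1], where d = p_A - p_P, se0 = sqrt[pbar(1 - pbar)(1/n_A + 1/n_P)] and se1 = sqrt[p_A(1 - p_A)/n_A + p_P(1 - p_P)/n_P].

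At f = 0: pbar = (106 x 0.20 + 53 x 0.05)/159 = 0.15, se0 = 0.0601, se1 = 0.0490, so power = Phi[(0.15 - 0.1177)/0.0490] = Phi(0.66), about 74%.

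| f | Tabulated incidence | Difference (points) | Power, all in denominator | Baseline-normal participants | Power, baseline-normal only |
|---|---|---|---|---|---|
| 0 | 20% vs 5% | 15 | 74% | 106:53 | 74% |
| 10% | 18% vs 4.5% | 13.5 | 68% | 95:48 | 69% |
| 20% | 16% vs 4% | 12 | 61% | 85:42 | 63% |
| 40% | 12% vs 3% | 9 | 46% | 64:32 | 49% |
| 60% | 8% vs 2% | 6 | 29% | 42:21 | 32% |
| 80% | 4% vs 1% | 3 | 13% | 21:11 | 16% |

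The ratio between arms stays 4:1 throughout. The absolute difference shrinks only if all participants form the denominator. Precision is lost either way.

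**The case against.** The strongest reply is that the plan captures deterioration by other routes. Protocol 8.1.1 lets an abnormal laboratory finding be an adverse event, and Protocol 8.3 records deterioration of a condition present at screening as one. SAP 9.2 names ALT increase among the adverse events to be reported with incidence and maximum severity, and SAP 10.2 summarizes events by arm, severity and relationship. All of this stands, and none of it needs a normal baseline. But an adverse event exists only if the investigator reports it, and the ALT entry sits under events of at least moderate severity judged possibly related. A table built from measured values is the check on that reporting.

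A reader might infer that worsening from an abnormal baseline is never counted anywhere. The SAP 9.2 categories, the hemoglobin analyses and the adverse event rules contradict that; the omission is confined to the SAP 10.4 table. A reader might also infer that participants were required to enter with abnormal values. Anemia is an and/or criterion, and the other limits only permit abnormal values.

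Two further points limit what can be said. SAP section 14 places table shells in a separate document, so shift tables there cannot be ruled out, although a shell would not alter the written definition. SAP 10.4 also notes that the DSMB tabulations were not focused on treatment emergence, but their layout is not given.

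**Conclusion.** The point holds for the SAP 10.4 incidence table. As defined, it gives no possible event to any participant whose baseline for that analyte was abnormal, and eligibility admits such participants. The practical gap is mainly in transaminases, bilirubin and creatinine, which have no objective categorical count including participants with an abnormal baseline.

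The size is unknown because the documents do not give baseline distributions. The power figures above rest wholly on assumed values of f and of a 20% versus 5% effect, and show direction only. It would be tempting to say that most of the trial is lost for hemoglobin, or that the arm comparison is biased toward no difference in every sense. The first has no figure behind it. The second is true only of the absolute difference with all participants in the denominator, since in the illustration the ratio is unchanged.

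This is a safety-reporting matter. The primary and key secondary efficacy analyses, the alpha and the sample size are unaffected. It is worth correcting because the rule as written gives a worse answer than an easily available alternative.

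**What to change.** In SAP 10.4:

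- For analytes with a CTCAE v4.0 grade (already the trial's grading system, Protocol 8.2.1), count as treatment-emergent any on-treatment value with a worse grade than baseline, using screening if baseline is missing, whether or not baseline was normal.
- Keep the present normal-to-abnormal rule for analytes without a grade, since the table covers every collected parameter. It can also stay as a secondary count for graded analytes.
- State the denominator for each analyte.
- Add baseline-to-worst-grade shift tables by arm, at least for ALT, AST, bilirubin, creatinine, hemoglobin, platelets and neutrophils.

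The cost is revised wording in one SAP section and a few extra tables from data already collected. Section 14 lets displays be added without an amendment if they do not contradict the SAP text. The change of definition does alter that text, so it should be made explicitly.
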